***Daily EPIC Report Elements:**

- Demographics: Patient name; MRN; CSN; Sex; DOB
- Hospital encounter data: Hospital admission date and time; Inpatient admission date and location; Reason for admission; Admission diagnosis; Admitting physician; Attending provider
- Interpreter needed – exclusion criterion
- Patient PCP
- Homeless status
- DRGs (Diagnosis Related Group): ICD10 F10 (Alcohol Use Disorders); F11 (Opioid Use Disorders); F19 (Other psychoactive substance use); Overdose
- CIWA (Clinical Institute Withdrawal Assessment)
- Flowsheet Data: RN Alcohol and Drug Screening Questions
 - CIWA Assessment
 - CIWA Score
 - Current alcohol usage information
 - Current drug usage information
 - Withdrawal risks
- Blood alcohol test
- Urine toxicology screen
- Past Medication orders: Buprenorphine; Naloxone; Naltrexone; Disulfiram; Acamprosate; Topiramate
- Social History: Alcohol usage; Drug usage

****Monthly EPIC Report Elements**

- Demographics: MRN; Age; Age at encounter; Date of Birth; Sex; Race; Ethnicity; City; Zip Code
- Hospital encounter data: Type; Dates; Disposition; Attending provider; PCP; Psychiatry consult;
- Diagnoses during encounter: ICD 10s: F10-F19; Problem list items
- CIWA Protocol and measure information
- Inpatient and discharge medication information: Suboxone; Buprenorphine; Subutex; Methadone; Naltrexone; Naloxone; Disulfiram; Acamprosate; Topiramate; Gabapentin; Narcan; Naloxone.
- Lab results: AST; ALT; GGT; Urine Toxicology Screen; Blood Alcohol Level
- Flowsheet Data: RN Alcohol Screening Questions
- Social History: Tobacco usage; Alcohol usage; Drug usage
- Family history of substance use disorder
- Notes: Physician, Nursing and Allied health Professional documentation
- Hospital Utilization Metrics: Length of Stay; Inpatient admissions in prior 12 months; ED admissions in prior 12 months; Number of 30-day readmissions

5.4 SOURCE DOCUMENTS

- Paper source documents include the patient informed consent form, if collected on paper. All other patient information and data will be entered directly into the REDCap database via computer or mobile device.
- Provider information will be collected via in-person or telephone interview which will be recorded and transcribed. There will be a NDA in place with the transcriber. The

transcriber will not be a part of the study team. With guidance from the Office of Research Administration, all appropriate agreements will be in place prior to the transcriber having any access to research materials. The interviews will take place only after the last patient has completed the study.

5.5 DATA COLLECTION AND STORAGE

- Patient data will be collected in hard copy and electronically, as previously described. All provider interviews will be recorded using a digitally-encrypted recorder and transcribed. There will be a Non-Disclosure Agreement in place with the transcriber.
- Paper consent forms will be stored inside a locked cabinet or locked office. Electronic data will be stored in a secure REDCap database. Recorded interviews will be stored on a digitally-encrypted recorder. Transcribed interviews will be uploaded to a secure file transfer protocol (SFTP) program such as Kiteworks.
- Only members of the study team will have access to study data. A limited data set will be transferred to RAND (collaborating institution) using SFTP programs and may include hospital and study visit dates, patient age, and patient zip codes.
- Linking files and identifiable information will be destroyed within a year after study completion. A limited data set will be retained for five years after study completion to allow ample time for analysis and publication.

5.6 CONFIDENTIALITY AND SECURITY OF DATA

As with any study that involves substance use, an additional risk of the proposed study is breach of confidentiality. Although this would be very serious if it were to occur, breach of confidentiality is unlikely. The hospital already has ample protections in place to protect patient privacy and we will protect interview and administrative data by using password-protected computers and encrypted files.

Verbal permission to discuss a subject's study participation in front of family members will be obtained. Written permission to discuss a subject's condition with family will be obtained as part of the consent form prior to any dissemination of a subject's information. One or more investigators with access to identifiable data are not at Cedars-Sinai, and the study team will work with the Office of Research Administration to execute an appropriate Data Use Agreement before sharing the limited data set.

6.0 DATA AND SAFETY MONITORING

6.1 DATA AND SAFETY MONITORING PLAN

I. Responsibility for Data Safeguarding

PI's [name] and [name] have joint responsibility for overseeing data safeguarding. They will train the designated CSMC approved study staff and project manager in data safeguarding techniques and will be responsible for the secure transmission of data from CSMC to secure research computers at RAND.

Additional oversight will be provided by our Data and Safety Monitoring Committee, consisting of [name] and [name] of CSMC. Drs. [name] and [name] will consult the committee as needed (e.g., to assess randomization issues, patterns of SAEs, etc.) during the course of the 6- 7- month data collection period. This committee is in lieu of a full DSMB due to the short data collection period and small patient size (N=80) of this

pilot study.

II. Risks associated with study participation

The collaborative care START intervention, called substance use treatment and recovery team (START) itself is inherently low-risk and therefore adverse events (AEs) experienced by study subjects are likely to be due to participants' underlying opioid and alcohol use disorders (OAUD) and other illnesses. Based on our prior research with this population, we expect depression and anxiety, medical illness and injury associated with OAUD, and, in some cases, unstable living conditions. Thus, adverse events may be related more to these underlying issues than to the START itself.

III. Handling of adverse events and serious adverse events and safety reporting

AEs and SAEs will be handled the same way in which hospital emergencies are handled. The hospital has several standard procedures in place for emotional or physical distress. If a client presents as suicidal, a social worker meets with him/her and then consults with a licensed mental health clinician (e.g., the CSMC PI [name]). The hospital will intervene as necessary, assess the client's state, and develop an appropriate plan. Clients with medical emergencies will be treated with usual hospital services. AEs occurring while the patient is hospitalized will be reported to PI [name]. AEs/SAEs occurring after discharge will be assessed by the START psychiatrist or care manager and reported to PI [name]. Incident reports will be written within one business day. All adverse and serious adverse events will be reported to the IRB and NIH according to CSMC IRB and NIH policies and procedures guidelines.

IV. Availability of trained personnel and referral resources

Prior to data collection [name] (or designee) will conduct training for the designated CSMC approved study staff and CSMC project manager. The training will address good clinical research practices, including data safeguarding and confidentiality. The approved study staff will be trained to promote standardized and objective collection and recording of participant information. All research staff will complete a human subjects protection course.

V. Procedures for data quality assurance and protecting confidentiality of participant data

A. Types of data needing safeguarding

- a. Patient contact information – name, telephone number, address, alternate contact information, entered on a tablet into an electronic record management system.
- b. Consent forms. Patients will provide written consent to participate in the study.
- c. Patient interview data – baseline and follow-up data from computer-assisted interview, entered on a tablet. (Appendix A).
- d. CSMC patient administrative data. Patient data obtained from the hospital electronic medical record (EPIC). (Appendix A).

B. Data sensitivity.

This study will collect participant names, phone numbers, addresses, and alternate contact information. These personal identifiers are necessary to obtain informed consent, to notify and contact participants about the follow-up interview and to conduct follow-up monitoring for patients in the START experimental arm of the study. A study ID connecting identifiable information with confidential data will be assigned to each participant. Signed consent forms and contact information will not be

stored in the same database forms as interview or administrative data.

C. Data safeguarding procedures

1. Patient contact information. CSMC will create a secure, encrypted and password-protected record management system using a secure, web-based system called Research Electronic Data Capture (REDCap) (see Appendix B). REDCap will allow the CSMC approved study staff to assign participant IDs to interviews, to maintain a link file between study ID and medical record number through a tablet that is securely linked to the web. REDCap is a secure, web-based tool used by CSMC researchers to build and manage surveys and databases. REDCap was developed at Vanderbilt University in Nashville, Tenn., and is available at no charge. It has become the primary standard for most Clinical and Translational Science Institutes (CTSIs), a national consortium of medical research institutions. The UCLA CTSI, to which Cedars-Sinai belongs, has helped support access to REDCap. There are two production websites — one that handles data that can be linked to an individual (known as protected health information, or PHI, under the federal HIPAA Privacy Rule) and another for non-patient-identified data. Research may build their own database after completing REDCap training or have the REDCap database developed at no charge. The link file will have read and write access restricted to approved study staff and the CSMC project manager.

2. Patient consent forms. If collected on paper, signed consent forms will be stored in a locked file cabinet at CSMC, separate from all study data.

3. Patient interview data.

a. Baseline. CSMC will also use REDCap to house the electronic computer-assisted patient interview. REDCap will allow the CSMC approved study staff to collect baseline data through a tablet that is securely linked to the web. The CSMC project manager will transmit baseline data (identifiable only by study ID) to RAND via secure file transfer protocol (SFTP) site. A program, such as PGP, that provides RSA-level security will be used to encrypt files. These data will not be shared with individuals who are not part of the project team, and no data shared with any members of the project study team will contain participant names.

b. 1-month follow-up. 1-month follow-up interview data will be collected by telephone, encrypted on a password-protected tablet that is connected to the survey through REDCap, only identified by study ID. Data will be collected by the CSMC approved study staff and entered directly into the secure tablet. The CSMC project manager will transmit baseline data (identifiable only by study ID) to RAND via secure file transfer protocol (SFTP) site. A program, such as PGP, that provides RSA-level security will be used to encrypt files. These data will not be shared with individuals who are not part of the project team, and no data shared with any members of the project study team will contain participant names.

4. CSMC administrative data. CSMC administrative data will be pulled from the electronic medical record system, EPIC, via a request submitted to the Research Informatics and Scientific Computing Core (RISCC). The CSMC project manager will replace all medical record numbers with study IDs. The CSMC project manager will then transmit the administrative data to RAND via the SSH File Transfer Protocol (SFTP) which is a network protocol that provides file access, file transfer, and file management functionalities over secure connection. It was designed by the Internet Engineering Task Force (IETF) as an extension of the Secure Shell protocol (SSH)

version 2.0 to provide secure file transfer capability.

D. Disclosure Risks

If private information about substance use is disclosed, possible psychological and social harm could result. However, the risk of such disclosure is rated as minimal given the safeguarding plan, and the magnitude of the harm were a breach of confidentiality to occur is likely to be little harm. We plan to minimize the possibility of a breach of confidentiality by instituting data safeguarding procedures as described above and maintaining identifiable data for only a limited period. We have several mechanisms in place to ensure data integrity and confidentiality. All data will be stored in a password-protected database. Paper files (i.e., consent forms) will be stored in locked file cabinets at CSMC, and electronic files will be stored in encrypted and password-protected files. Furthermore, electronic files transmitted to the RAND research team will be identified only by participant ID numbers. Identifying information linking patients to their study ID number will be retained in an encrypted and password protected record management system at CSMC. Confidentiality policies and procedures will be reviewed with all new staff.

E. Destruction of Data

Consent forms will be retained at CSMC for three years after completion of the study. Linking files and identifiable information will be destroyed within a year after study completion. A limited date set will be retained for five years after study completion to allow ample time for analysis and publication.

VI. Stopping rules for clinical trial

We will employ the following stopping rule for the clinical trial: if there is clear evidence of harm. Although we do not expect any physical harms or serious psychological harms beyond minimal distress, we have several procedures for monitoring harm from the intervention, including asking participants to contact us if they experience any adverse events, offering additional resources to those with very high levels of mental health symptoms and problem drinking or drug use, and providing resources after baseline and at follow-up. We do not expect there to be overwhelming evidence of the benefit of START during this pilot study due to the small sample size, but we will monitor this and stop the trial if this is indicated. We also do not expect that there will be no likelihood of demonstrated treatment benefit (futility) for the intervention as compared to control.

6.2 QUALITY CONTROL AND QUALITY ASSURANCE

- PI [name] and the quantitative analysis team will be responsible for evaluating data for adherence with the protocol and for accuracy in relation to source documents.
- PI [name] and the quantitative analysis team at RAND will be responsible for evaluating data quality. Reports generated from the database will provide a basis for ongoing monitoring of subject accrual and retention, as well as completeness of data. These will be used to identify and resolve problems that may arise. EPIC data will be exported and checked monthly during the study and survey data will be transmitted and checked monthly. Under the direction of a statistician, a quantitative analyst will check the data for completeness.

- Fidelity to intervention methods may be monitored and assessed by anonymous audio recording of up to 5% of intervention sessions of subjects randomized to the intervention arm. Patient confidentiality will be maintained by 1) uploading recordings to a secure Box folder; 2) allowing access to the Box folder by only one RAND study co-investigator ([name]); 3) ensuring recordings will be listened to in Box and not downloaded or saved; 4) ensuring recordings are deleted after listening. Verbal permission to record the session will be obtained from subjects prior to the start of recording.

7.0 STATISTICAL CONSIDERATIONS

7.1 STUDY OUTCOME MEASURES

Although we do not anticipate that this pilot study will be sufficiently powered to detect treatment effects, we will estimate models with the primary goals of learning the variance of the treatment effect estimator, which will be used in power calculations for future study design, and detecting areas of potential concern. This model would look for differences in outcomes between intervention (START) and control (UC) conditions, controlling for baseline measure of the outcome, where appropriate, using a generalized linear modeling-based framework. For dichotomous outcomes, we will employ a logistic regression model of the form $Pr(yyii = 1) = 1/(1 + \exp(-(\beta\beta_0 + \beta\beta_1xxii + \beta\beta_2zzii)))$. Here i indexes individuals, $\beta\beta_0$ represents the overall intercept, $xxii$ represents the treatment status of individual i , 0 for control, and 1 for intervention, and $\beta\beta_1$ is the effect of the intervention. The variable $zzii$ represents the baseline measure and $\beta\beta_2$ associated coefficient. Continuous outcomes will be modeled using linear regression. We will also perform exploratory analyses to investigate whether there are subgroups that may be responding better or worse to the intervention by interacting the covariates in Table 2 with the treatment indicator. Because there will be nearly as many potential covariates as observations, we will employ the “horseshoe prior” in Bayesian analyses of the outcome.⁶⁴ Qualitatively, this model starts from the assumption that most (if not all) of the covariates are unimportant for predicting the outcome, and attempts to learn which covariates are important. The intention is not so much to detect significant differences, but rather to highlight areas of potential concern. For example, if individuals with high pain levels respond less well to START recipients, this exploratory approach could draw attention to potential issues that could be optimized ahead of a future trial.

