and treatment initiation.¹⁷⁻²¹ Pharmacotherapies to address AUDs (acamprosate, oral and injectable naltrexone, and disulfiram) and OUDs (buprenorphine/naloxone, methadone, and oral and injectable naltrexone) are effective for use across medical settings²²⁻²⁸ but are seldom administered in hospitals or recommended as part of follow-up care.^{29,30} New research demonstrates that initiating buprenorphine/naloxone in the emergency department with follow-up in primary care for patients with OUDs can increase SUD treatment entry and abstinence,³¹ and that inpatients with complications from OUDs are amenable to initiating medication in the hospital and being linked with follow-up care.³² The current standard of care for hospitalized patients with OAUDs is screening, brief intervention outcomes for people with moderate to severe AUDs or for people with OUDs.^{33,34,16,35} Two possible reasons are that SBIRT does not incorporate MAT initiation or address the needs of those needing more than a brief intervention prior to referral. Barriers to initiating MAT for hospitalized patients may include lack of OAUD treatment expertise on the medical team and absence of a patient-centered, measurement- and population-based system for assessing and treating patients with OAUDs. Embedding a collaborative care team (START) for inpatients with OAUDs within an existing hospital consultation-liaison psychiatry service could improve MAT initiation and linkage to follow-up care and clinical outcomes, and, ultimately, reduce 90-day readmission rates.

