3.2 INCLUSION CRITERIA

1. Inpatient at CSMC
2. Age 18 and older
3. Screens positive for moderate to severe OAUDs based on the alcohol and opioid questions on the World Health Organization (WHO) Alcohol, Smoking, and Substance Involvement Screening test (ASSIST).⁴⁵ Patients with scores >10 for alcohol or >3 for opioid use will be eligible for the study
4. Speaks English as primary language
5. Willing to participate in, and able to provide contact information for, telephone follow-up calls and follow-up interview
6. Able to provide informed consent

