5.0 DATA COLLECTION AND MANAGEMENT

5.1 DATA PROCUREMENT

- Recruitment information will be procured through physician referral, or through review of an existing daily EPIC workbench report* of opioid and alcohol misuse.
- Administrative outcomes will be procured through a monthly EPIC report.**
- Patient Baseline Survey Measures will be procured through patient interviews and will be recorded on a tablet or computer into a web-based survey system (REDCap).
- Some demographic and all diagnosis variables will be procured from eligibility screener conducted in REDCap. (Eligibility screener variables from all patients that screen will be used to assess study feasibility. Data from patients not enrolled in the study will be anonymous, i.e., they will not be linked to an MRN or any identifying information.)
- Patient Follow-up Survey Measures will be procured through a telephone interview by 1-month after the patient is discharged from the hospital. During collection of contact information at the baseline visit, patients may opt-in to receive text message reminders about this interview. These reminders will be sent via Twilio SMS through REDCap and will not contain any identifying information regarding the patient or the specific study.
- Provider Survey Measures will be procured through provider interviews and will be recorded and transcribed.

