5.3 VARIABLES COLLECTED

- The following data points/variables will be collected:

Baseline Measures:

Variable	Source Document
Demographics 
 • Age • Sex (Biological at Birth) • Gender (Identity) • Race/ethnicity • Housing status • Marital status • Income • Education 	Demographics Form
Mental Health Symptoms 
 • Depression • Anxiety 	PHQ-9 survey ^{51,52} GAD 7 survey ⁵³⁻⁵⁵
Pain intensity and frequency	PEG ⁵⁶
Alcohol/Opioid Diagnosis	WHO ASSIST ⁵⁷
30-day Alcohol/Opioid Use: National Survey on Drug Use and Health 30-day use questions	Patient Survey (Adapted from NSDUH ⁵⁸)
SUD Treatment Utilization	Patient Survey (Adapted from NSDUH ⁵⁸)
Healthcare Utilization Related to SUD	Patient survey (Adapted from GAIN ⁵⁹)
Employment	Patient Survey
Negative Consequences	Short Inventory of Problems Alcohol and Drugs (SIP-AD) ⁶⁰
Patient Experience of Stigma	Adapted from Grosso et al. 2019. ⁶¹ Questions to assess stigma experience.
Self- Stigma	Substance Abuse Stigma Scale (SASS) ⁶²
Receipt of START Intervention Components (Patient)	
START Intervention Received (Assessment, Engagement, Treatment/Discharge Planning); Length of Intervention (hours)	START Patient Registry
START Intervention Follow Up Received (Number of follow up calls made)	START Patient Registry

Follow-up Survey Measures (Patient)	
Mental Health Symptoms 
 Anxiety Depression 	PHQ-9 Survey ^{51,52} GAD 7 Survey ⁵³⁻⁵⁵
30-day Alcohol/Opioid Use: National Survey on Drug Use and Health 30-day use questions	Patient Survey (Adapted from NSDUH ⁵⁸)
SUD Treatment Utilization	Patient Survey (Adapted from NSDUH ⁵⁸)
Healthcare Utilization Related to SUD	Patient survey (Adapted from GAIN ⁵⁹)
Negative Consequences	Short Inventory of Problems Alcohol and Drugs (SIP-AD) ⁶⁰
Employment	Patient Survey
Patient Experience of Chronic Illness Care	PACIC ⁶³
Satisfaction with START intervention	Patient Survey
Provider Interviews (Provider)	
Acceptability/feasibility of START Intervention (Provider Interview Guide)	Provider Interview Guide

Outcome Measures:

Outcome	Measure, Assessment (Type of Variable)	Data Source
Primary Outcomes		
In-hospital MAT initiation	Received an OAUD MAT between admission and discharge (Binary)	CSMC admin data
Linkage to follow-up care	Received at least one visit post-discharge for MAT and/or psychosocial care for OAUD (Binary)	Appointment dates 1-month interview

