Past 30-day frequency of heavy drinking days and/or all days of any opioid use	Days of use in the past 30 – Adapted National Survey of Drug Use and Health (NSDUH) ⁵⁸ (Continuous)	Baseline interview 1-month interview
Secondary Exploratory Outcome		
90-day readmission to CSMC	Readmitted to CSMC up to 90-days after discharge during study period	CSMC admin data
Covariates		
Sociodemographics	Gender, sex, age, race/ethnicity, income, education, occupational status, marital status, zip code, homelessness in past six months.	Eligibility screener; Baseline interview
OAUD diagnosis	Moderate or Severe, ASSIST ⁴⁵	Eligibility screener
Pain Level	Pain level between 1-10; Pain interference level between 1-10, PEG ⁵⁶ (Continuous)	Baseline interview 1-month interview
Primary and secondary diagnosis (inpatient stay)	Medical or mental health conditions as determined by the inpatient physician (Categorical)	CSMC admin data
Length of hospital stay	Number of days of hospital stay (Continuous)	CSMC admin data
Intervention “dose”; exposure	Amount time spent with patient (Continuous)	START Registry
Insurance	Payer name	CSMC admin data

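### Optional: the main model for in-hospital MAT initiation is in effect unadjusted, although alcohol versus opioid is known before randomisation and could be added as one covariate

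*Combined protocol and SAP*

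**What the plan says.** The logistic model in section 7.1 has an intercept, a treatment indicator and one further term, the baseline measure. The comparison is made "controlling for baseline measure of the outcome, where appropriate, using a generalized linear modeling-based framework". The same section gives the purpose: to learn the variance of the treatment effect estimator for later power calculations, and to detect areas of concern, in a pilot that is not expected to be powered.

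The first primary outcome (5.3) is "Received an OAUD MAT between admission and discharge (Binary"). Section 3.3 excludes patients currently on approved medication for either disorder. The second, linkage, is at least one post-discharge visit for medication or psychosocial care. Section 5.3 lists SUD treatment utilisation as a baseline survey measure, but no text names it as the baseline measure for linkage.

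On substance, section 3.2 sets separate cut-offs: "Patients with scores >10 for alcohol or >3 for opioid use will be eligible for the study". Section 5.1 adds: "Some demographic and all diagnosis variables will be procured from eligibility screener conducted in REDCap". Section 4.0 places randomisation after consent and the baseline interview, and its text mentions no stratification.

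The covariate list in 5.3 describes OAUD diagnosis as "Moderate or Severe, ASSIST", which is severity, and also includes inpatient diagnosis. Covariates other than the baseline measure enter only the exploratory interaction analyses, under a prior that "starts from the assumption that most (if not all) of the covariates are unimportant for predicting the outcome".

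**The concern.** The only adjustment in the main model is for the baseline value of the outcome, and for MAT initiation that value does not vary. Both binary outcomes pool patients with alcohol and opioid use disorders. Section 1.0 lists largely different medications for the two (naltrexone is common to both), so different uptake is plausible, though the documents give no rates by disorder.

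What is at stake is precision and the planning variance. If substance predicts MAT initiation, the crude risk difference has a larger variance than one standardised over substance. The exploratory analyses may show that substance is prognostic, but they leave the main estimate and its variance as they are. Reporting both variances would let the next trial be planned with or without adjustment.

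**Working it through.** **The plan's own figure.** 2 × 40 = 80 and 16 per month × 5 months = 80. No power, event rate or variance is stated, so there is nothing further to reproduce.

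**Step 1: the model reduces.** With the baseline term constant, the design matrix (intercept, treatment, baseline) has rank 2, not 3. The third coefficient cannot be estimated, and the model is intercept plus treatment.

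**Step 2: assumptions.**
- 40 per arm (7.2).
- Opioid share p: 719/(1,037 + 719) = 719/1,756 = 0.409 from the 2014 admissions in 7.2, ignoring overlap; 0.20 as an alternative.
- Usual-care rate 10% in alcohol patients; effect +20 points in both disorders; gap g of 0, 20, 30 or 50 points between disorders. None of these is in the documents.

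**Step 3: large-sample ratio, simple allocation.** Let a = 0.1 + p·g, b = a + 0.2 and C = a(1−a) + b(1−b). The crude variance is C/40 and the standardised variance is (C − 2g²p(1−p))/40.

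For p = 0.409 and g = 0.30: a = 0.223, b = 0.423, C = 0.1732 + 0.2440 = 0.4172. The deduction is 2 × 0.09 × 0.409 × 0.591 = 0.0435. The ratio is 0.4172/0.3737 = 1.12.

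**Step 4: simulation at n = 80.** 12,000 trials per setting, additive logistic model with a two-level substance term, risk difference by standardisation, Firth fit only where the ordinary fit was not finite.

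| Gap (points) | Crude/standardised variance, 41% opioid: formula | simulated | 20% opioid: formula | simulated |
|---|---|---|---|---|
| 0 | 1.00 | 0.99 | 1.00 | 0.99 |
| 20 | 1.05 | 1.04 | 1.04 | 1.02 |
| 30 | 1.12 | 1.09 | 1.09 | 1.07 |
| 50 | 1.35 | 1.34 | 1.25 | 1.25 |

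Both estimators average 0.20, so neither is biased. At 41% opioid the true SEs are 9.9, 10.2 and 10.7 points (crude) against 9.8, 9.8 and 9.3 (standardised) at gaps of 20, 30 and 50.

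**Step 5: the odds-ratio scale.** Adding substance raises the SE of the log odds ratio from 0.54 to 0.57, 0.51 to 0.56 and 0.48 to 0.61 at gaps of 20, 30 and 50, because the adjusted odds ratio is a conditional and larger quantity. Power does not fall with it: at a 50-point gap it goes from about 46% to 55%. In a separate calculation with a conditional odds ratio of 3, power went from 46% to 52% at usual-care rates of 10%/40% (alcohol/opioid), and from 60% to 59% at 20%/20%.

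**Step 6: misclassification.** Suppose 30% are truly opioid patients, and 25% of the rest are coded as opioid while keeping alcohol rates. The gain then falls to about 1% to 2% at a 20-point gap, 3% at 30 and 13% to 14% at 50.

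**Step 7: if allocation is stratified by substance.** Figure 1 is not available to check. In that case the true variances are nearly equal (ratio 1.00 to 1.01), but the crude model reports a variance too large by about 3%, 9% or 29% at gaps of 20, 30 or 50 (41% opioid).

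**The case against.** The strongest reply is that the plan contains no error. It adjusts for baseline only where that is appropriate, which already covers an outcome without one, and it disclaims power. That stands, and it is why the point is optional.

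Second, the planned quantity is a log odds ratio, and on that scale the proposal raises the SE. This also stands: the smaller variance belongs to a standardised risk difference, which the plan does not mention. It does not follow that nothing is gained, since the adjusted test keeps or gains power when substance is prognostic (step 5).

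Third, the rates are invented, and the gain is small unless the gap is large. One pilot measures it poorly: the ratio of the two estimated variances has a 95% range of 0.96 to 1.26 at a 20-point gap (41% opioid). This stands as a limit on what the pilot can show. So does the caution that an opioid score above the cut-off may include patients whose main disorder is alcohol.

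Fourth, linkage is a weaker case. It counts psychosocial care, and baseline treatment utilisation could serve as its baseline measure. This stands.

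Fifth, the exploratory analyses and retained data already allow a look at substance, and stratum proportions could be tabulated later. That is true, but a prespecified term avoids choosing the adjustment after seeing the data.

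A reader might infer that the crude comparison is biased, or that chance imbalance in substance invalidates it. Randomisation rules that out. A reader might also infer that substance goes unrecorded because the covariate row gives only severity. The separate cut-offs in 3.2 and the baseline ASSIST item in 5.3 show that it is recorded.

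**Conclusion.** This holds as an optional improvement for MAT initiation. The main model for that outcome is in effect unadjusted, and a pre-randomisation variable of plausible prognostic value is already collected. The benefit lies in the risk-difference variance and in test power, and it serves the plan's goal of learning a variance for the next trial. It is not a gain in the SE of the planned log odds ratio.

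Under simple allocation the size is 2% to 9% at gaps of 20 to 30 points and 25% to 35% only at 50, less if the opioid code misclassifies. It would be wrong to read the upper figure as expected: nothing in the documents supports a gap that large. If allocation is stratified by substance, precision barely changes, and the benefit is that the variance is no longer over-reported. The third primary outcome, days of use, has a true baseline measure and is not affected.

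**What to change.** In section 7.1:
- **MAT initiation:** prespecify a two-level substance covariate from the ASSIST screener (opioid score above the eligibility cut-off, versus alcohol only) as a main effect. Report arm-specific proportions and the substance-standardised risk difference with its interval and variance, beside the planned unadjusted odds ratio. Use a Firth fit if the ordinary fit is not finite.
- **Linkage:** name baseline SUD treatment utilisation as the baseline measure. A substance term there is secondary.
- **Interpretation:** state that the adjusted odds ratio is conditional, has a larger SE and is not to be compared with the unadjusted one.

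Avoid three levels (alcohol only, opioid only, both). If 10% have both disorders, that fit was not finite in 3% to 37% of simulated trials, against at most about 5% with two levels.

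The cost is SAP wording and one parameter, from data already collected. If substance is not prognostic, the risk-difference variance is about 1% larger. The delta-method variance of the standardised risk difference ran 3% to 7% low at this sample size under simple allocation, so a bootstrap interval is a sensible check.
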